Study design	
This is an international, non-interventional research study of adult patients with FD and their caregivers. The study will comprise a prospective time and motion evaluation and a cross-sectional evaluation of patient and caregiver-reported outcomes. Patients' demographic characteristics will be collected from hospital medical records.
 
For the cross-sectional evaluation of patient and caregiver-reported outcomes, patients with FD and their caregivers will be asked to complete a series of questionnaires, to include validated measures of HRQoL, wellbeing and work productivity (for patients) and work productivity and the strain of care provision (for caregivers). Patients and caregivers will also complete a bespoke questionnaire to evaluate the total time associated with attending the hospital or treatment centre for a single ERT administration visit, and time away from work. In addition, patients will also be asked about their level of fatigue using a bespoke Likert scale. With the exception of the work productivity questionnaire and Fatigue Likert scale, the study questionnaires will be completed at a single point in time, when the patient attends the hospital or treatment centre for administration of ERT. The work productivity questionnaire (which has a recall period of seven days, excluding the day of completion) will be completed twice; the first work productivity questionnaire will be completed 1-7 days after receiving a dose of ERT (ideally within 2 days), to capture a seven day period that includes an ERT administration visit and the second questionnaire will be completed on the day the patient attends the hospital or treatment centre to receive their next dose of ERT (to capture a seven day period that does not include ERT administration). The Fatigue Likert scale will be completed three times; during an ERT administration visit, on the evening of the visit and the next day.

	Separate patient consent will be obtained for the time and motion evaluation and for the cross-sectional evaluation of patient-reported HRQoL, wellbeing, levels of fatigue and work productivity; thus, patients who do not wish to complete the study questionnaires will remain eligible for the time and motion study (and vice versa), provided that consent has been obtained.

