Enzyme replacement therapies (ERT) with agalsidase alfa (Replagal®, Shire) and with agalsidase beta (Fabrazyme®, Sanofi Genzyme) currently represent two treatment options for patients with FD and have been shown to reduce substrate levels in several cell types. In addition there are reports of reductions in the severity of neuropathic pain, stabilization of renal and cardiac function and delay in the occurrence of serious complications^{7–10}. However, both ERT preparations need to be administered as an intravenous (IV) infusion every two weeks and therefore lifelong ERT places a considerable burden on patients, their caregivers and healthcare services. ERT administered in the hospital or clinic setting requires frequent visits for IV infusions, which many patients find stressful and inconvenient; furthermore, hospital-based treatment often takes place in a specialist FD centre, which may be a considerable distance from the patient's home^{11,12}. In some countries ERT can be administered in the patient's home under certain circumstances (for example, if the patient has stable disease and experienced no adverse reactions during hospital-based infusion) and this is generally perceived to be more convenient than hospital-based therapy^{11–13}, can improve treatment compliance¹⁴ and may help to reduce the burden on healthcare services. However, even home-based ERT administration can cause disruption to a patient's daily activities and usually requires a healthcare professional (HCP) to supervise the infusion. To mitigate risk of adverse effects associated with ERT, patients are also frequently administered pre-medications with antihistamines and low-dose corticosteroids, which can be an added burden to patients.

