- The strain of providing care for a patient with FD will be assessed using the CSI. The CSI consists of 13 items and measures the strain of care provision in five domains (financial, physical, psychological, social and personal)²³. It takes approximately 5 minutes to complete.

Patients and caregivers will also complete a bespoke questionnaire to evaluate the total time associated with attending the hospital or treatment centre for a single ERT administration visit, costs (i.e. out of pocket expenses) and time away from work. In addition, patients will also be asked about their levels of fatigue using a single-item bespoke Likert scale. Bespoke questionnaires will be designed specifically for the purpose of the study.

It is estimated that it will take approximately 25-30 minutes in total for patients to complete their questionnaires (including the second WPAI) and 15-20 minutes for caregivers to complete their questionnaires (including the second WPAI:CG).

Patient questionnaires will be presented in the following order: bespoke Fatigue Likert scale (first completion), SF-12, WHO-5, bespoke patient questionnaire (to be started during the ERT visit and finished at home), bespoke Fatigue Likert scale second and third completion (to be completed on the evening of the ERT administration visit and the next day), WPAI first completion (to be completed at home between 1 and 7 days after the ERT infusion [ideally in first 2 days]), WPAI second completion (to be completed on the day of the patient's next ERT administration visit). Caregiver questionnaires will be presented in the following order: CSI, bespoke caregiver questionnaire (to be started during the ERT administration visit and finished at home), WPAI:CG first completion (to be completed at home between 1 and 7 days after the ERT infusion), WPAI:CG second completion (to be completed on the day of the patient's next ERT administration visit).

The full schedule for completion of the study questionnaires for patients and caregivers is provided in Table 3 below.

Table 3. Timeline of completion and list of questionnaires administered to patients and caregivers

Participant group	Timeline of questionnaire completion			
	During ERT infusion visit	Evening of ERT infusion	1-7 days after ERT infusion	Day of next ERT infusion (~15 days after previous infusion)

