
Summary measures of patients':
 
 • HRQoL (SF-12 scores / responses). • General wellbeing (WHO-5 scores / responses). • Level of fatigue (bespoke Fatigue Likert scale). • Levels of work impairment (WPAI scores / responses). 
Questionnaire scores and/or item responses will be reported using summary statistics, as appropriate to the questionnaire and in accordance with the licensed scoring manual / instructions for use.
	
 • Patient SF-12, WHO-5, Fatigue Likert scale and WPAI responses and dates of completion. For the bespoke Fatigue Likert scale, times (hours and minutes) of completion will also be recorded.

Secondary objective 4: To describe work productivity (measured by the WPAI:CG) and the strain of care provision (measured by the CSI) in caregivers of patients with FD treated with ERT.
	

Summary measures of caregivers':
 
 • Levels of work impairment (WPAI:CG scores / responses). • Levels of strain of providing care for a patient with FD (CSI scores / responses). 	
 • Caregiver WPAI:CG and CSI responses and date of completion.

Questionnaire scores and/or item responses will be reported using summary statistics, as appropriate to the questionnaire and in accordance with the licensed scoring manual / instructions for use.
	

Patients' demographic and clinical characteristics (all patients)
	

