9.11 Limitations of the research methods

- Patient and caregiver consent is a requirement of this study; this may introduce selection bias and result in a study sample that may not be representative of the wider patient and caregiver population of interest.
- Centres will be selected on the basis of interest in taking part in the study and experience in treating patients with FD with ERT. It is acknowledged that these centres may not be representative of current wider clinical practice in the countries of study.
- For patient- and caregiver-reported outcomes, the data will rely on the completeness of the answers provided by participants, which will not be queried or otherwise followed up to clarify inconsistencies or omissions and may be subject to reporting bias.
- A limitation of asking patients to complete questionnaires during their ERT infusion is that they may feel more anxious and/or tired when they are attending the hospital to receive treatment than at other times; consequently, the descriptions of patient-

reported HRQoL and general wellbeing obtained in the study may be an overestimate of the overall impact of FD.

- This is a descriptive study and no analyses to control for confounding will be carried out. For ethical reasons, time and motion data will not be stratified by individual staff member, although the performance of staff may be a factor in any observed variability. Experience levels of staff performing tasks observed in the study may vary between centres and may not reflect the experience level of staff performing the same tasks outside the study centres. There are also likely to be differences between the participating countries in local clinical protocols, healthcare settings and care processes, which may introduce variability in the data collected.
- It is acknowledged that the time and motion evaluation may not capture the full burden of ERT administration since first infusions (which are expected to take longer than subsequent infusions) are excluded from the study; this is because the longer first infusion represents only a one-off burden at the start of long-term (potentially lifelong) treatment.
- It is also acknowledged that QoL data could be impacted by ERT episodes that are close in timing to each other.

10. Other aspects

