
Summary measures of patients':
 
 ○ HRQoL (SF-12 scores/ responses) ○ General wellbeing (WHO-5 scores / responses). ○ Level of fatigue (bespoke Fatigue Likert scale). ○ Levels of work impairment (WPAI scores / responses) ○ For the bespoke Fatigue Likert scale, times (hours and minutes) of completion will also be recorded. 	
Questionnaire scores and/or item responses will be reported using summary statistics, as appropriate to the questionnaire and in accordance with the licensed scoring manual / instructions for use.
 
For these scores, the total of all items in each of these will be summarized as per section 2.5 for quantitative variables. The frequency and percentages of responses for individual items will also be given. HRQoL and Who-5 will be given for baseline (the data collected during ERT infusion visit). Fatigue score will be given for baseline and the change scores from baseline to score collected at the same day evening of ERT infusion and 15 days after 1st infusion. WPAI scores will be given one at 1-7 days after infusion and change from this to 15 days after infusion.
 
The summary statistics of completion time in minutes will be calculated as per section 2.5 for quantitative variables.

---	---

Secondary objective 4

To describe work productivity (measured by the WPAI:CG) and the strain of care provision (measured by the CSI) in caregivers of patients with FD treated with ERT.

Summary measures of caregivers':
	
Questionnaire scores and/or item responses will be reported using summary statistics, as appropriate to the questionnaire and in accordance with the licensed scoring manual / instructions for use.

---	---

 ○ Levels of work impairment (WPAI:CG scores / responses). ○ Levels of strain of providing care for a patient with FD (CSI scores / responses). 	
The total scores will be summarized as per section 2.5 for quantitative variables. The individual item responses will be presented using frequency and percentages.
 
WPAI-CG will be summarized at 1-7 days after 1st infusion and change from this to 15 days after infusion.
 
CSI scores collected during ERT infusion will be summarized.

Patients' demographic and clinical characteristics (all patients)	

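### The fatigue baseline is only required to fall within the ERT visit, so the planned change scores can mix pre-treatment ratings with ratings made after pre-medication or during infusion

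*SAP*

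**What the plan says.** **SAP, section 2.6, secondary objective 3.** The fatigue analysis reads: "Fatigue score will be given for baseline and the change scores from baseline", first to the rating made that evening and then to a rating about 15 days after the infusion. Baseline is explained only for the other two instruments: "HRQoL and Who-5 will be given for baseline (the data collected during ERT infusion visit". No separate definition is given for fatigue. The completion time of the fatigue scale is to be summarised as a quantitative variable and is put to no other use.

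**Protocol, section 4 (Abstract, Study design).** "The Fatigue Likert scale will be completed three times; during an ERT administration visit, on the evening of the visit and the next day". Table 3 gives the same schedule and places the first rating in the column for the infusion visit.

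**Protocol, section 9.1.2.** The scale heads the pack: "Patient questionnaires will be presented in the following order: bespoke Fatigue Likert scale (first completion), SF-12, WHO-5". The order is not tied to arrival, pre-medication or the start of infusion.

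**Protocol, section 9.7.** The validated questionnaires (apart from the first work productivity form) are expected to be filled in while the infusion runs. Where part of the episode takes place at home, all the questionnaires are likely to be completed there.

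**Protocol, section 9.6, Table 4.** "For the bespoke Fatigue Likert scale, times (hours and minutes) of completion will also be recorded". The patient questionnaire also records when the infusion started. Pre-medication times are on the time and motion form.

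**Protocol, section 9.11.** Of patients answering during the infusion it says "they may feel more anxious and/or tired when they are attending the hospital to receive treatment than at other times". The consequence is drawn for HRQoL and wellbeing only.

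**The concern.** A change from baseline describes what happens over an ERT visit only if the baseline precedes the part of the visit that might alter the score. Here the baseline window is the whole visit. Section 7 of the protocol says that "patients are also frequently administered pre-medications with antihistamines and low-dose corticosteroids", so a rating made after pre-medication, or well into the infusion, may already carry part of the effect that the later ratings are compared with.

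The limitations section recognises a timing problem for HRQoL and wellbeing, for which the SAP plans no change score. It does not mention fatigue, for which the SAP does plan one.

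What is at stake is the meaning of the reported change. If fatigue is already raised at the first rating, the change to the evening or the next day is understated. Section 9.9.2 of the protocol has the data analysed by country and product, and the expected infusion times differ by product, so the mix of early and late baselines may differ between the two products.

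**Working it through.** The plan gives no sample size, effect size or standard deviation for fatigue, so there is no planned figure to reproduce. The check has three parts.

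**1. Does anything fix the first rating before treatment?**
- Abstract and Table 3: at some time during the visit.
- Section 9.1.2: first in the pack, with no clock anchor for the pack.
- Section 9.7: where part of the episode is at home, completion at home is likely, which can put the first rating after set-up or during the infusion.
- SAP section 2.6: the completion time is summarised but not compared with pre-medication or infusion start.
- Sections 9.10 and 9.9.4: no queries are raised on patient-reported data, and no sensitivity analyses are planned.

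The timing is therefore open, and a late first rating would enter the baseline unmarked.

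**2. Size of the possible shift.** Let f be the share of first ratings made after pre-medication or infusion start, and d the fatigue shift already present in those ratings (positive means more tired). Relative to a true pre-treatment baseline,

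shift in mean change = -f × d.

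Neither f nor d is in the documents. Assumed values:

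| f | d = 0.25 | d = 0.5 | d = 1 |
|---|---|---|---|
| 0 | 0 | 0 | 0 |
| 0.5 | -0.13 | -0.25 | -0.50 |
| 1 | -0.25 | -0.50 | -1.00 |

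Units are points on the fatigue scale. The same shift enters every later change score, because all use the same baseline. If d were negative the signs would reverse.

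**3. How much of the visit lies after infusion start?** Inputs are the ranges in protocol section 9.8: pre-administration 10-30 minutes, post-administration 15-30, infusion 40-60 (alfa) and 90-180 (beta). The midpoints are 20, 22.5, 50 and 135.
- Alfa total: 20 + 50 + 22.5 = 92.5 minutes. Beta total: 20 + 135 + 22.5 = 177.5 minutes. Both match the overall means in Table 5.
- Share after infusion start, alfa: (50 + 22.5) / 92.5 = 78%. Range: 55/85 = 65% to 90/100 = 90%.
- Share after infusion start, beta: (135 + 22.5) / 177.5 = 89%. Range: 105/135 = 78% to 210/220 = 95%.

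These would be the shares of late ratings only if the first rating fell at a random time in the visit. That is an assumption, and being first in the pack makes it a pessimistic one. The calculation shows that most of the permitted window is late and that the share differs by product.

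**The case against.** The strongest reply is that late completion is permitted only by silence. The scale is first in the pack, so sites may well hand it out on arrival, and then the bias is zero. The sentence in section 9.7 about completion during infusion names the validated questionnaires, and the fatigue scale is a bespoke one. The questionnaire text and the data collection guidelines are not available for review and may contain a timing instruction. All of this stands. It makes the bias possible, not demonstrated.

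A second reply is that the objective is to describe fatigue, with no hypothesis and no planned comparison between treatments. A change from visit to evening is a legitimate description if it is labelled as that, and the SAP also reports the distribution of responses. This also stands. A reader might infer that the change score is biased as a matter of fact, or that it cannot be interpreted at all. The documents support neither inference, since they give no share of late ratings and no size of shift.

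A third reply is that section 9.11 speaks of attending hospital in general. Tiredness from travel or anticipation would be present on arrival too, so an earlier rating would not remove it. That is correct and limits what the fix can achieve.

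A fourth reply concerns exclusion. With about 30 questionnaire sets per country, an even split between products gives about 15 per cell. Dropping half would leave 7 or 8, below the group size of 10 under which percentages are normally not reported. Late raters should therefore not be dropped.

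None of these replies supplies the missing anchor for the baseline.

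**Conclusion.** The point holds as a weakness in definition. The SAP takes change from a baseline that the protocol fixes only to the visit, so pre-treatment and mid-treatment ratings can be pooled under one label, and the recorded clock time is not used to separate them. The resulting shift in mean change is -f × d: zero if every first rating precedes treatment, and between -0.13 and -1.00 point across the assumed cases with at least half rated late and a shift of 0.25 to 1 point. These figures rest entirely on assumed values of f and d. The true size is unknown.

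The consequence is confined to a descriptive secondary endpoint. The primary endpoint, HCP time, is unaffected. The correction is worth making because it is cheap and turns the score into a clear before-and-after contrast.

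The same SAP sentence contains a firmer inconsistency. It takes a fatigue change to about 15 days after the infusion, whereas the protocol collects the third rating the next day and none at the following infusion visit. The two must be reconciled.

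**What to change.** **Protocol, section 9.1.2 and Table 3.** State that the first Fatigue Likert scale is completed on arrival, before any pre-medication or infusion, and keep it first in the pack. Put the same line on the questionnaire.

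**SAP, section 2.6.**
- Define the fatigue baseline explicitly.
- Flag a first rating as late by comparing its recorded completion time with the infusion start on the patient questionnaire. Both are already collected from questionnaire participants.
- Add pre-medication start to the comparison where the patient also consented to time and motion and that visit was observed. The two components have separate consent, so this cannot be done for everyone.
- Report the change for all patients, and separately for those with a pre-infusion first rating, with the number in each group.
- Correct the time point of the second fatigue change score so that SAP and protocol agree.

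**Protocol, section 9.11.** Extend the limitation to fatigue, noting that a general effect of attending the visit remains even with a rating on arrival.

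**Cost.** One extra instruction at the visit, one SAP rule and one extra table, some of whose country-by-product cells may be small. If data collection is already complete, the SAP rule can still be applied alone.

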Patients with FD	
 • Bespoke Fatigue Likert scale • SF-12 • WHO-5 • Bespoke patient questionnaire (to be started during ERT infusion visit and finished at home) 	
 • Bespoke Fatigue Likert scale 	
On Day 1 after ERT infusion:
 
 • Bespoke Fatigue Likert scale 
Any day 1-7 after ERT infusion:
 
 • WPAI 	
 • WPAI
Caregivers of patients with FD	
 • CSI • Bespoke caregiver questionnaire (to be started during ERT infusion visit and finished at home) 	-	
Any day 1-7 after ERT infusion:
 
 • WPAI:CG 	
 • WPAI:CG

SF-12: Short Form-12 questions, WHO-5: World Health Organisation 5 questions, WPAI: Work Productivity and Activity Impairment, CG: Caregiver.

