9.3 Study time periods

It is anticipated that the prospective recruitment / data collection period for this study will be approximately 4-5 months, starting from the date on which the relevant approvals to conduct the study are in place. Ideally, a maximum of two episodes of care per patient during the data collection period will be included for the time and motion evaluation (except in exceptional cases where it is determined that it is required to observe three episodes per patient due to a limited number of available patients/episodes for observation). Patients with FD and their caregivers will be asked to complete the study questionnaires once during the data collection period, when the patient attends the hospital or treatment centre for administration of ERT; the exception is the work productivity questionnaire, which will be completed on two occasions and the bespoke Fatigue Likert scale, which will be completed on three occasions (as described above). Separate patient consents will be obtained for the time and motion evaluation and cross-sectional questionnaire completion so patients will have the option to take part in only one or both parts of the study, according to their preference.

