9.5 Patient identification, sampling and recruitment

Adult patients with FD who are receiving treatment with ERT will be identified from local databases and pharmacy records by members of the whole care team at each centre and assessed for eligibility in line with the inclusion criteria. Patients will be approached by a member of their care team, given information about the study and invited to consent to participate. Patients may be approached in advance of their next scheduled attendance for ERT administration (by telephone and/or post) or in person, at a routine hospital visit. If patients do not wish to complete the study questionnaires they are still eligible for the time and motion study (and vice versa), provided that consent for the relevant component of the study has been obtained. For patients who are eligible to be observed more than once (for the time and motion study), initial consent for observation of up to three episodes of care will be obtained, and will be confirmed verbally by their HCP before the second and third episode of care. Each patient will only be asked to complete one set of questionnaires (with the exception of the work productivity questionnaire, which will be completed twice and the bespoke Fatigue Likert scale, which will be completed three times), even if they contribute more than one episode of care to the time and motion study.

Caregivers will only be invited to participate in the study if the patient whom they care for also consents to study participation. Caregivers will be approached for consent when they attend the hospital or treatment centre with the patient for their ERT administration visit.

Consecutive eligible patients (and their caregivers) presenting at the participating centres during the prospective recruitment period will be included in the study until the required sample size is reached. It is anticipated that patient and caregiver recruitment will take place over a 4-5 month period, starting from the date on which the relevant approvals needed to conduct the study are in place.

Prior to commencement of data collection, HCPs at the participating centres (and community healthcare facilities, where relevant) who are involved in the administration of ERT will be identified and asked to provide consent to be observed in their provision of care. Consent from HCPs will be confirmed by the observer verbally before each episode of care.

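### SAP 2.6 plans a fatigue change score at 15 days, when no fatigue rating is scheduled, and does not name the next-day rating that the protocol collects

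*SAP*

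**What the plan says.** SAP section 2.6, under Secondary objective 3, sets the time points for each patient questionnaire. For fatigue it asks for the baseline score, meaning the rating at the infusion visit, and "change scores from baseline to score collected at the same day evening of ERT infusion and 15 days after 1st infusion". The sentence after it deals with the WPAI: the score at 1-7 days after the infusion, then the change to 15 days.

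The protocol gives the fatigue schedule in several places, always the same:

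- Abstract, Study design: "The Fatigue Likert scale will be completed three times; during an ERT administration visit, on the evening of the visit and the next day".
- Section 9.1.2, on the second and third ratings: "to be completed on the evening of the ERT administration visit and the next day".
- Table 3, patient row: the third rating stands under "On Day 1 after ERT infusion". In the column for the day of the next infusion, about 15 days later, the WPAI is the only patient questionnaire.
- Section 9.3: "the bespoke Fatigue Likert scale, which will be completed on three occasions".
- Section 9.5: each patient fills in "the bespoke Fatigue Likert scale, which will be completed three times), even if they contribute more than one episode of care".

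The scale has one item. Section 9.1.2 states that "patients will also be asked about their levels of fatigue using a single-item bespoke Likert scale".

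**The concern.** The SAP and the protocol disagree about when the third fatigue rating is taken. Followed literally, the SAP asks for a change score that the study has no scheduled data to produce, and it does not say whether or how the next-day rating is to be reported. That rating is the only one that shows fatigue beyond the day of infusion.

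Mislabelling is also possible, though this is inference. The SAP names three fatigue time points and the dataset will hold three ratings per patient. A programmer who pairs third with third would present a next-day result as a 15-day result. Completion dates and times are recorded (Protocol Table 4), so the slip could be found. However, SAP section 3.2 limits independent review to the primary endpoint and plans no other analysis checks.

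**Working it through.** The plan gives no figure to reproduce here. The check sets the two schedules side by side and then counts.

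| Time point | Fatigue collected (Protocol 9.1.2, Table 3) | Fatigue named in SAP 2.6 |
|---|---|---|
| During infusion visit | Yes | Yes, as baseline |
| Evening of the visit | Yes | Yes, as change from baseline |
| Next day (Day 1) | Yes | No |
| About 15 days | No | Yes, as change from baseline |

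**Could a 15-day rating come from elsewhere?**

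1. *From a second observed episode.* No. Protocol section 9.5 holds the fatigue scale at three completions per patient however many episodes are observed.
2. *From the third rating being given at the next visit.* No. Section 9.1.2 and Table 3 put it on the day after the infusion. Section 9.9.1 groups the second and third ratings with the forms filled in after leaving the clinic.
3. *From a schedule revised in the SAP.* Nothing in the SAP signals a change, and an analysis plan cannot supply a rating that the protocol does not collect.

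**Does the SAP name Day 1 elsewhere?** No. Fatigue otherwise appears only in the objectives (section 1.2 and the heading of Secondary objective 3), without time points.

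**Counts.** The inputs are three ratings per patient (Protocol 9.1.2) and about 120 patient questionnaire sets, 30 in each of 4 countries (SAP 2.4).

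- Fatigue change scores named: 2. With scheduled data: 1 (evening). Without: 1 (15 days).
- Ratings at full completion: 120 × 3 = 360.
- Ratings after the visit rating: 120 × 2 = 240.
- Day 1 ratings: 120, which is 120/360 = 1/3 of all ratings and 120/240 = 1/2 of those after the visit rating.
- Scheduled ratings at 15 days: 0.

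The documents give no return rate for the Day 1 form. If 70% to 100% are returned (an assumption), the ratings without a named time point number 0.70 × 120 = 84 to 120.

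**The case against.** The mismatch itself is not in dispute. The case on the other side is that it matters little.

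- *It is probably a slip in one label.* The next SAP sentence uses 15 days correctly for the WPAI, so the label may have been carried across. That is plausible but unproven, and the sentence is still the operative instruction for this endpoint.
- *Day 1 may be covered anyway.* SAP 2.6 also says, without naming time points, that total scores are summarised and item responses tabulated. With a single item, that could include a Day 1 description. This stands, and it limits the concern. It does not supply a Day 1 change score, and it leaves the reporting to the analyst.
- *The protocol asks for no change score.* True: Protocol Table 4 asks only for summary measures of fatigue. But once the SAP chooses change scores, they should be ones that can be computed.
- *An empty result would be seen.* SAP 2.3 requires the number in each analysis to be stated, so a blank 15-day row should be noticed. That would not by itself put Day 1 in its place.
- *An n of zero is a prediction.* Fair. What the documents establish is that no rating is scheduled at 15 days. Forms completed after leaving the clinic may also come back later or be taken by telephone. A stray late entry would still not be a planned 15-day rating.
- *The counts are one fact multiplied by 120.* Also fair. They show how many ratings are involved, not a bias or a loss of precision.
- *A single Likert item is ordinal.* SAP 2.5 describes ordinal variables by frequencies, or medians and IQR, while 2.6 treats these scores as quantitative. This is a separate matter, but worth settling in the same edit.

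**Conclusion.** The concern holds. SAP 2.6 names a fatigue change score for which the protocol schedules no rating, and it omits the Day 1 rating that the protocol does schedule. One of the two named change scores cannot be produced from scheduled data. Up to 120 Day 1 ratings, about 30 per country, have no named place in the analysis.

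The 120 rests on the planned number of questionnaire sets and full completion. The inconsistency rests on neither, only on the text of the two documents.

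The consequence is limited. The study is descriptive, one part of one secondary objective is affected, the visit-to-evening change is sound, and no data are lost. It should be corrected before analysis. It is not a threat to the study.

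**What to change.** In the fatigue sentence of SAP 2.6, replace the 15-day time point with the next day (Day 1) after the infusion, in line with Protocol section 9.1.2 and Table 3. State that fatigue is reported at the three collected time points (visit, evening, Day 1), with the evening-minus-visit and Day 1-minus-visit changes. Say also how a single ordinal item and its change are to be summarised under SAP 2.5. Leave the WPAI sentence as it is, since its 15-day point agrees with Table 3.

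The cost is a few words. No new data collection or protocol change is needed, because the Day 1 rating is already scheduled. The SAP appendix still lists the table shells as to be confirmed, so no finished shell has to be redone.
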